Patients randomized to the INTELLiVENT-ASV group received this mode of ventilation immediately after the admission in the ICU. Quickwean was immediately activated at that time, but the SBT mode was switch off for the first three hours of mechanical ventilation. It was not possible to extubate the patient without consulting the ICU physician on duty, who made the final call to extubate. Spontaneous breathing trials (SBT) were not applied during the first three hours of mechanical ventilation. The patient was extubated without a SBT if the physicians decided that the patient could be extubated within the first three hours of mechanical ventilation. After the first three hours of ventilation the SBT function

of INTELLiVENT-ASV was initiated and the patient could be extubated if the patient had a successful SBT of at least 10 minutes with a consultation of the ICU physician on duty. The standard operating procedure is described in appendix 2.

In both arms it was possible to deviate from protocol if the ICU physician deemed it necessary for the safety of the patient. In these cases the patient could be switched to the not allocated mode.

In both arms the same alarm settings were used, which were: 1) pressure alarm ≥ 35 cmH₂O; 2) expiratory minute volume alarm ≤ 3.0 and ≥ 15.0 L/min; 3) respiratory rate alarm ≥ 35 breaths per min; 4) tidal volume alarm ≥ 900 ml; 5) apnea time alarm ≥ 30 seconds; 6) EtCO₂ alarm ≤ 30 and ≥ 60 mmHg; and 7) SpO₂ alarm $\leq 90\%$.

Outcomes

Primary outcome:

1. Percentage of time (during at least 30 seconds) in the unacceptable zone according to the total postoperative ventilation time on the ICU during the first three hours of ventilation or until extubation, if extubated earlier.

Secondary outcomes:

1. Percentage of time (during at least 30 seconds) in the optimal and acceptable zone according to the total postoperative ventilation time during the first three hours of ventilation or until extubation, if extubated earlier.
2. Percentage of breaths in the optimal, acceptable and unacceptable zone according to the total number of recorded breaths during the first three hours of ventilation or until extubation, if extubated earlier.

3. Percentage of time (during at least 30 seconds) in the optimal, acceptable and unacceptable zone according to the total number of recorded time.
4. Percentage of breaths in the optimal, acceptable and unacceptable zone according to the total number of recorded breaths.

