5. Ventilator variables and vital signs will be reported after each half an hour from ICU admission until spontaneous breathing (>5 consecutive spontaneous breaths) or the first three hours of mechanical controlled ventilation. Ventilator variables include the manually measured tidal volume, driving pressure and mechanical power. Driving pressure will be calculated by extracting the PEEP after >5 seconds of an expiratory hold from the plateau pressure level after >5 seconds of an inspiratory hold. Both this recorded PEEP and plateau pressure were used with other manually recorded parameters to calculate the mechanical power:

$$\text{Power}_{rs} = RR \cdot \{\Delta V^2 \cdot [0.5 \cdot EL_{rs}] + (RR \cdot ((1+I:E)/(60 \cdot I:E)) \cdot R_{aw})\} + \Delta V \cdot PEEP\}. [6]$$

Vital signs include also EtCO₂: PaCO₂ and PaO₂: FIO₂ ratio that were conducted at admission and after approximately an hour of ventilation.
6. The number patients extubated in the first six, twelve and twenty-four hours after surgery without a reintubation or non-invasive ventilation ≤48 hours after extubation for respiratory insufficiency (a successful extubation).
7. Ventilation time considered as the time from intubation during surgery until first and first successful extubation adjusted by the duration of surgery.
8. Weaning duration considered as the time from stopping intravenous sedatives and a rectal temperature of ≥35.5°C since admission on the ICU until successful extubation.

9. The time from intubation during surgery until spontaneous breathing (at least ≥ 5 consecutive spontaneous breaths) adjusted by the duration of surgery.
10. The time from stopping intravenous sedatives with a rectal temperature of $\geq 35.5^{\circ}\text{C}$ during admission on the ICU until spontaneous breathing (at least ≥ 5 consecutive spontaneous breaths).
11. The total number of alarms and interventions per hour within the first 3 hours or until extubation.
12. The total number of alarms and interventions per hour according to the total registered ventilation time.
13. ICU mortality
14. 30 day mortality
15. The number of ICU readmissions during the first 72 hours after ICU discharge.
16. ICU length of stay.
17. The number of agitated moment, established by the nurse at the bedside.
18. The number of bolus administration of sedatives and analgesics.

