replications. If a very nonsymmetrical distribution is found, we will use the best distribution that fits the data.

Percentage of breaths in the optimal, acceptable and unacceptable zone according to the total number of breaths during the first three hours of ventilation or until extubation, if extubated earlier, and according to the postoperative total recorded ventilation time. (eTable 4).

The percentage of breaths in the three zones will be reported as number and percentages (according to the total number of breaths and not according to the number of patients) and the effects of the intervention will be estimated with risk ratio and 95% confidence intervals calculated with Wald's likelihood ratio approximation test and with χ^2 tests for hypothesis testing.

Number of successful extubations within the first 6, 12 and 24 hours after surgery (eTable 5).

The effects of the intervention on the number of successful extubation within the first 6, 12 and 24 hours of mechanical ventilation after admission on the ICU will be reported as number and percentages and estimated with risk ratio and 95% confidence intervals calculated with Wald's likelihood ratio approximation test and with χ^2 tests for hypothesis testing. These findings will be confirmed using logistic models adjusted by the duration of surgery, total intravenous sedatives dosage and the time from ICU admission until a rectal temperature $>35.5^{\circ}\text{C}$.

Total Time until extubation (considering the time from ICU admission until extubation) (eTable 5).

The time until extubation will be assessed using Kaplan–Meier curves, and hazard ratios with a 95% confidence interval will be calculated with Cox proportional hazard models without adjustment for covariates. The proportional hazard assumptions will be tested and alternative parametric survival models will be used if the proportionality assumption is not sustained. These findings will be confirmed using Cox proportional hazard models adjusted by the duration of surgery, total intravenous sedatives dosage and the time from ICU admission until a rectal temperature $>35.5^{\circ}\text{C}$.

Time until first spontaneous breathing (considering the time from ICU admission until first spontaneous breathing) (eTable 5).

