The time until first spontaneous breathing will be assessed using Kaplan–Meier curves, and hazard ratios with a 95% confidence interval will be calculated with Cox proportional hazard models without adjustment for covariates. The proportional hazard assumptions will be tested and alternative parametric survival models will be used if the proportionality assumption is not sustained. These findings will be confirmed using Cox proportional hazard models adjusted by the duration of surgery the duration of surgery, total intravenous sedatives dosage and the time from ICU admission until a rectal temperature $>35.5^{\circ}\text{C}$.

The total number of alarms and intervention within the first 3 hours or until extubation (eTable 5).

The total number of alarms and intervention within the first 3 hours or until extubation will be reported as mean \pm standard deviation and median (interquartile range). The effect of the intervention will be estimated with a

Student's *t*-test and reported as the mean difference between the two groups.

The consistency of the findings of the Student's *t*-test will be tested using a bootstrapped Student's *t*-test with 1,000 replications. If a very nonsymmetrical distribution is found, we will use the best distribution that fits the data.

ICU mortality (eTable 5).

The effects of the intervention on ICU mortality rate will be reported as number and percentages and estimated with risk ratio and 95% confidence intervals calculated with Wald's likelihood ratio approximation test and with χ^2 tests for hypothesis testing.

ICU readmission (eTable 5).

The effects of the intervention on ICU readmission rate will be reported as number and percentages and estimated with risk ratio and 95% confidence intervals calculated with Wald's likelihood ratio approximation test and with χ^2 tests for hypothesis testing.

30-Day mortality (eTable 5).

Survival within 30 days will be assessed using Kaplan–Meier curves, and hazard ratios with a 95% confidence interval will be calculated with Cox proportional hazard models without adjustment for covariates. The proportional hazard assumptions will be tested and alternative parametric survival models will be used if the proportionality assumption is not sustained.

ICU length of stay (eTable 5).

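### The supporting extubation models adjust for total sedative dose with no time window, and subgroup 1 splits the primary outcome by time to extubation; both can condition on consequences of the allocated mode.

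*Combined protocol and SAP*

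**What the plan says.** **Supporting models.** In the SAP's outcome analyses, three secondary outcomes have an unadjusted lead analysis followed by adjusted models that are meant to confirm it:

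- Successful extubation within 6, 12 and 24 hours: "logistic models adjusted by the duration of surgery, total intravenous sedatives dosage and the time from ICU admission until a rectal temperature" above 35.5°C.
- Time until extubation: "Cox proportional hazard models adjusted by the duration of surgery, total intravenous sedatives dosage" and the same temperature variable.
- Time until first spontaneous breathing: models "adjusted by the duration of surgery the duration of surgery, total intravenous sedatives dosage" and the same temperature variable.

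None of these sections says when the dose total starts or ends.

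**Timing.** Under The ventilation strategies: "Patients randomized to the INTELLiVENT-ASV group received this mode of ventilation immediately after the admission in the ICU". Secondary outcome 8 is defined as "Weaning duration considered as the time from stopping intravenous sedatives and a rectal temperature of" at least 35.5°C, counted on the ICU, and outcome 10 starts from the same point ("The time from stopping intravenous sedatives with a rectal temperature of" at least 35.5°C). Outcome 18 is "The number of bolus administration of sedatives and analgesics". The treating team was not blinded (Randomization and blinding).

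**Subgroup 1.** The Subgroup analyses section divides the primary-outcome analysis into patients successfully extubated before and after the median postoperative ventilation time. The eTable 6 shell has columns for effect estimate, 95% CI and p value. Subgroup effects are to be judged by interaction in zero-inflated generalized linear models and shown in a forest plot. Time from ICU admission to extubation is itself an analysed outcome.

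**The concern.** A confirmatory model should adjust for variables that the intervention cannot have changed. Sedation is stopped on the ICU, after the mode has begun, so a total dose can contain an amount that depends on the arm or simply on how long the patient stayed ventilated. In the second case the covariate is partly a consequence of the outcome, and conditioning on it absorbs some of the treatment effect. An attenuated adjusted HR would then be read as failure to confirm. Because the window is not stated, it could also be chosen after the data are seen.

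Subgroup 1 has the same structure. Which half a patient falls into is known only after treatment. If the mode shortens ventilation, each half compares differently selected patients by arm, and a within-half p-value can be read as a treatment effect when it partly reflects that selection.

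**Working it through.** The plan states no figure to reproduce for either part. What follows is illustration on assumed inputs, apart from the planned difference (14.0 min), the SD (10.0 min) and the three-hour window, which the SAP gives.

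**Part 1: sedative covariate**

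Assumed: 98 patients per arm (half of 196); Weibull time to extubation, shape 2, median 5 h; conditional HR 1.5; log-HR -0.3 per SD for duration of surgery and for log time to temperature, the latter unaffected by arm. Pre-ICU dose is a random rate times duration of surgery. Tracking ICU dose is a random rate times the time to 2 h before extubation (correlation with ventilation time 0.78). There were 1,200 runs per cell.

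| Cox model, time to extubation | HR | p<0.05 |
|---|---|---|
| Unadjusted (the result to be confirmed) | 1.44 | 71% |
| Surgery + temperature, no dose | 1.52 | 80% |
| + dose, all pre-ICU | 1.52 | 80% |
| + dose, ICU sedation ends at temperature threshold | 1.52 | 79% |
| + dose, 25% tracks ventilation time | 1.45 | 68% |
| + dose, 50% tracks | 1.36 | 53% |
| + dose, 100% tracks | 1.30 | 43% |

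The unadjusted 1.44 lies below 1.52 because leaving out prognostic covariates pulls a hazard ratio towards 1. The fair benchmark for bias is therefore 1.52, and the benchmark for apparent confirmation is 1.44.

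The other two outcomes show the same order for the five dose scenarios:

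- Spontaneous breathing (median 3 h): HR 1.52, 1.52, 1.46, 1.37, 1.31.
- Logistic model at 6 h: OR 1.92 unadjusted, 2.06 without dose; with dose 2.08, 2.06, 1.97, 1.77, 1.61.
- Logistic model at 12 h (shape 1.2): OR 2.36 unadjusted, 2.68 without dose; with dose 2.68, 2.67, 2.50, 2.12, 2.00.
- At 24 h (99.3% v 97.5% extubated) about 98 × 0.007 + 98 × 0.025 ≈ 3 patients are not extubated, too few to fit the model.

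A separate simulation with different assumptions agrees in direction. With dose accumulating over ventilation time, the HR is 1.40 unadjusted, 1.18 adjusted for total dose and 1.43 adjusted for pre-ICU dose only. If the mode lowers ICU dose by 0.5 SD and acts only through dose, the three are 1.14, 0.95 and 1.15.

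**Part 2: subgroup 1, no true effect on the primary outcome**

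1. On the percentage scale over 180 minutes, the planned effect is 14/180 = 7.78 points and the SD is 10/180 = 5.56 points.
2. An HR of 1.5 at Weibull shape 2 shifts log time by ln(1.5)/2 = 0.203. The SD of log time is (π/√6)/2 = 0.641, or 0.675 with the two covariates. The shift δ is therefore 0.203/0.675 = 0.30 to 0.203/0.641 = 0.32 SD.
3. With a normal outcome that has correlation ρ with ventilation time, splitting at the pooled median gives a spurious arm difference in each half of ρ × SD × φ(δ/2) × [1/Φ(-δ/2) - 1/Φ(δ/2)].
4. At δ = 0.30 the last two factors multiply to 0.191; at δ = 0.316, to 0.201.
   - ρ = 0.3: 0.3 × 5.56 × 0.191 = 0.32 points.
   - ρ = 0.5: 0.5 × 5.56 × 0.201 = 0.56 points.
   - As a share of 7.78 points: 4% to 7%.
5. The early half holds 98 × Φ(0.15 to 0.16) ≈ 55 v 43 patients instead of 49 v 49. The standard error of the within-half difference is about 1.0 to 1.1 points, so p<0.05 occurs in about 6-8%.
6. In this normal model the bias has the same sign and size in both halves, so it cancels in their difference. The simulated interaction test rejects in 5.0-5.8% of runs.

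**The case against.** **Limited reach.** The lead analyses are unadjusted, and the adjusted models only support secondary outcomes. Subgroup inference is planned by interaction, which is largely protected. All of this stands.

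**Part 1 shows an open definition, not a demonstrated bias.** No passage says that the mode changes sedation, and an unblinded team makes that possible only. Pairing the end of sedation with a temperature threshold in outcomes 8 and 10 hints at the harmless case, though it does not establish it. Nothing supports the assumption that sedation runs until 2 h before extubation. At 25% tracking the HR (1.45) still matches the unadjusted 1.44. Appendices 1 and 2, with the operating procedures, are not in the available text and may describe sedation. These points make the bias conditional. They do not supply a window, and total dose read plainly includes ICU dose.

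**Stronger readings that a reader might infer:**

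- *The adjustment sets contradict each other.* Outcome 7 is ventilation time "until first and first successful extubation adjusted by the duration of surgery", and outcome 9 likewise names only surgery. But both clocks start at intubation during surgery, while the supporting Cox models start at ICU admission. Different covariates are not in themselves a contradiction.
- *The subgroup bias reaches 0.90 points, with 59 v 39 patients in the early half and 14% false positives.* That needs a 0.5 SD shift, which at shape 2 implies an HR of about 1.9 (exp(2 × 0.5 × 0.641)), more than the 1.5 used in part 1.
- *The temperature covariate is contaminated too.* It is measured after the mode starts, but the documents show no route from ventilation mode to rewarming.

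**Conclusion.** The concern holds in conditional form. As written, the three sets of supporting models may include sedative dose given under the allocated mode. Depending on how that dose relates to ventilation time, the adjusted HR runs from no bias (1.52) to below the unadjusted result (1.36 or 1.30 against 1.44). If dose is pre-ICU only, or ICU sedation ends at the temperature threshold, there is no bias, and the SAP should say which applies.

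The within-half comparisons in eTable 6 are not randomised comparisons if the mode changes ventilation time. At an extubation HR of about 1.5 the distortion is modest: 0.3 to 0.6 points per half and 6-8% false positives. If the mode does not change ventilation time, there is none. The calculation uses a normal outcome, whereas the SAP plans zero-inflated models, so the figures are orders of magnitude.

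The documents do not support reading this as a threat to the main result. The primary t-test, the lead unadjusted Cox and χ² analyses, and subgroups 2 and 3 (fixed by ICU admission) are untouched. The change should be made because it is cheap, with medium confidence that it will matter in these data.

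**What to change.** **Supporting models.** For all three outcomes, define the sedative covariate as dose given before ICU admission. If that was not recorded, drop it. Keep duration of surgery. Time to the temperature threshold may stay; a sensitivity model without it is optional, as is reporting ICU sedative dose by arm.

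**Subgroup 1.** Mark it and eTable 6 as a descriptive post-randomisation split and remove the within-half between-arm p-values. If it stays in the forest plot, label it there in the same way.

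**Cost.** SAP wording for three outcomes and one table before database lock, with no new data. One prespecified table is downgraded. If pre-ICU dose was not recorded, chance imbalance in it cannot be adjusted for. Assuming it predicts extubation (log-HR -0.3 per SD), dropping it lowers power in the supporting Cox model from 79% to 74% (HR 1.50 to 1.47). In the same runs, keeping total dose with 25%, 50% or 100% tracking gives 67%, 52% or 36%.

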Visual inspection of histograms and D'Agostino–Pearson's normality tests will be used to assess continuous distribution of the data. For the conventional ventilation and INTELLiVENT-ASV arms, the baseline characteristics will be expressed as counts and percentages, means and standard deviations (SD), or medians and interquartile ranges (IQR) whenever appropriate. Hypothesis tests will be two-sided with a significance level of 5%. We will not adjust P -values for multiple comparisons. Analyses will be performed using the R (R Core Team, 2016, Vienna, Austria) program.

Trial profile: Patient flows will be presented in a CONSORT flowchart (Figure 1).

Baseline comparisons: Patient's baseline characteristics will be presented by study arm (eTable 2).

Adherence to study interventions and, ventilator variables and vital signs:

Ventilatory variables and vital signs will be reported from ICU admission until extubation or up to the first 72hours of recorded mechanical ventilation time (eTable 3). These variables, including driving pressure and mechanical power, will be compared among the groups using Student's *t* test. Also, the trend of the ventilator variables every 30 minutes for the first three hours will be compared between the groups using mixed-effect linear models, considering an interaction term between time and group and the patients as random effects.

Outcomes:

Percentage of time in the optimal, acceptable and unacceptable zone for at least 30 seconds during the first three hours of ventilation or until extubation, if extubated earlier, and according to the postoperative total recorded ventilation time (eTable 4).

The number of episodes where the ventilation stays in one of the three zone for at least 30 consecutive seconds will be calculated. Then, this number will be corrected by the total duration of ventilation as:

$$\%_{UZ} = (T_{UZ} / DV) \times 100$$

Where $\%_{UZ}$ is the percentage of time in a zone, T_{UZ} is the time in seconds where the ventilation stays in the specific zone for at least 30 consecutive seconds, and DV is the total duration of ventilation in seconds. This number will be reported as mean \pm standard deviation and median (interquartile range). The effect of the intervention will be estimated with a Student's *t*-test and reported as the mean difference between the two groups. The consistency of the findings of the Student's *t*-test will be tested using a bootstrapped Student's *t*-test with 1,000

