Acceptable zone	Mean ± SD	Mean ± SD	Mean difference		Mean ± SD	Mean ± SD	Mean difference		Mean ± SD	Mean ± SD	Mean difference	
Median (IQR)	Median (IQR)	Median (IQR)	Mean difference		Median (IQR)	Median (IQR)	Mean difference		Median (IQR)	Median (IQR)	Mean difference	
Unacceptable zone	Mean ± SD	Mean ± SD	Mean difference		Mean ± SD	Mean ± SD	Mean difference		Mean ± SD	Mean ± SD	Mean difference	
Median (IQR)	Median (IQR)	Median (IQR)	Mean difference		Median (IQR)	Median (IQR)	Mean difference		Median (IQR)	Median (IQR)	Mean difference	

eTable 5 – Secondary outcomes	Intention-to-treat				Per-protocol			
	INTELLiVENT-ASV	Conventional mode	Effect Estimate (95% CI)	P value	INTELLiVENT-ASV	Conventional mode	Effect Estimate (95% CI)	P value
Ventilation time								
Intubation – successful extubation*	Mean ± SD Median (IQR)	Mean ± SD Median (IQR)	Mean difference		Mean ± SD Median (IQR)	Mean ± SD Median (IQR)	Mean difference	
ICU admission – successful extubation*	Mean ± SD Median (IQR)	Mean ± SD Median (IQR)	Mean difference		Mean ± SD Median (IQR)	Mean ± SD Median (IQR)	Mean difference	
Weaning time								
Stop sedation – successful extubation*	Mean ± SD Median (IQR)	Mean ± SD Median (IQR)	Mean difference		Mean ± SD Median (IQR)	Mean ± SD Median (IQR)	Mean difference	
Time until spontaneous breathing**								
Intubation – spontaneous breathing	Mean ± SD Median (IQR)	Mean ± SD Median (IQR)	Mean difference		Mean ± SD Median (IQR)	Mean ± SD Median (IQR)	Mean difference	
ICU admission – spontaneous breathing	Mean ± SD Median (IQR)	Mean ± SD Median (IQR)	Mean difference		Mean ± SD Median (IQR)	Mean ± SD Median (IQR)	Mean difference	
Stop sedation – spontaneous breathing	Mean ± SD Median (IQR)	Mean ± SD Median (IQR)	Mean difference		Mean ± SD Median (IQR)	Mean ± SD Median (IQR)	Mean difference	
Mortality								
ICU	N / Total (%)	N / Total (%)	Risk ratio		N / Total (%)	N / Total (%)	Risk ratio	
30-day	N / Total (%)	N / Total (%)	Hazard ratio		N / Total (%)	N / Total (%)	Hazard ratio	
Length of stay								
ICU	Mean ± SD Median (IQR)	Mean ± SD Median (IQR)	Mean difference		Mean ± SD Median (IQR)	Mean ± SD Median (IQR)	Mean difference	
ICU readmissions								
Readmission <72 hours after discharge	N / Total (%)	N / Total (%)	Risk ratio		N / Total (%)	N / Total (%)	Risk ratio	
Number of alarms								
First 3 hours (n/3 hours)	Mean ± SD Median (IQR)	Mean ± SD Median (IQR)	Mean difference		Mean ± SD Median (IQR)	Mean ± SD Median (IQR)	Mean difference	

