All recorded time (n/hour) Median (IQR)	Mean ± SD Median (IQR)	Mean ± SD Median (IQR)	Mean difference	Mean ± SD Median (IQR)	Mean ± SD Median (IQR)	Mean difference
Times SpO₂ measurement of <85% during mechanical ventilation*						
First 3 hours (n/3 hours) Median (IQR)	Mean ± SD Median (IQR)	Mean ± SD Median (IQR)	Mean difference	Mean ± SD Median (IQR)	Mean ± SD Median (IQR)	Mean difference
All recorded time (n/hour) Median (IQR)	Mean ± SD Median (IQR)	Mean ± SD Median (IQR)	Mean difference	Mean ± SD Median (IQR)	Mean ± SD Median (IQR)	Mean difference
Lowest measured SpO ₂ over all recorded time.	Mean ± SD Median (IQR)	Mean ± SD Median (IQR)	Mean difference	Mean ± SD Median (IQR)	Mean ± SD Median (IQR)	Mean difference
Missing measurement**: all recorded time EtCO ₂	Mean ± SD Median (IQR)	Mean ± SD Median (IQR)	Mean difference	Mean ± SD Median (IQR)	Mean ± SD Median (IQR)	Mean difference
SpO ₂	Mean ± SD Median (IQR)	Mean ± SD Median (IQR)	Mean difference	Mean ± SD Median (IQR)	Mean ± SD Median (IQR)	Mean difference
Number of interventions						
First 3 hours (n/3 hours) Median (IQR)	Mean ± SD Median (IQR)	Mean ± SD Median (IQR)	Mean difference	Mean ± SD Median (IQR)	Mean ± SD Median (IQR)	Mean difference
All recorded time (n/hour) Median (IQR)	Mean ± SD Median (IQR)	Mean ± SD Median (IQR)	Mean difference	Mean ± SD Median (IQR)	Mean ± SD Median (IQR)	Mean difference
Pulmonary complication (first 72 hours)						
Pneumonia	N / Total (%)	N / Total (%)	Risk ratio	N / Total (%)	N / Total (%)	Risk ratio
Pneumothorax	N / Total (%)	N / Total (%)	Risk ratio	N / Total (%)	N / Total (%)	Risk ratio
Atelectasis	N / Total (%)	N / Total (%)	Risk ratio	N / Total (%)	N / Total (%)	Risk ratio
Overall	N / Total (%)	N / Total (%)	Risk ratio	N / Total (%)	N / Total (%)	Risk ratio
Acceptance score						
Score (1-10) Median (IQR)	Mean ± SD Median (IQR)	Mean ± SD Median (IQR)	Mean difference	Mean ± SD Median (IQR)	Mean ± SD Median (IQR)	Mean difference

*Measurement with a quality index >50%

** Measurement with a quality index <51%

eTable 6 – Intention-to treat analysis and per protocol analysis of the percentage of breaths and time in the optimal, acceptable and unacceptable zones during the first 3 hours of postoperative mechanical ventilation or extubation, and for all recorded breaths for patient who were successfully extubated before or after the median postoperative mechanical ventilation time.

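### Alarms and interventions are defined as an hourly rate, but the analysis rule compares totals over a window that extubation can shorten

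*Combined protocol and SAP*

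**What the plan says.** The plan describes this endpoint in three places.

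- **Outcomes, secondary outcome 11** defines a rate: "The total number of alarms and interventions per hour within the first 3 hours or until extubation". Outcome 12 is also a rate, over a longer period: "The total number of alarms and interventions per hour according to the total registered ventilation time".
- **Predefined statistical analysis plan, paragraph on alarms and interventions**, states: "The total number of alarms and intervention within the first 3 hours or until extubation will be reported as mean" with SD, and as median with IQR. The effect is estimated by Student's t-test and "reported as the mean difference between the two groups". A bootstrapped t-test checks consistency, and another distribution may be used if the data are very asymmetric. The paragraph mentions no hourly division, offset or exposure term.
- **eTable 5** labels the early-window rows for alarms and for interventions "First 3 hours (n/3 hours". The rows for the whole recording are labelled "All recorded time (n/hour".

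Two other passages bear on this. Under The ventilation strategies, in both arms, the physician could decide that "the patient could be extubated within the first three hours of mechanical ventilation". For time in the ventilation zones, over the same window, the SAP does adjust for exposure: "Then, this number will be corrected by the total duration of ventilation as", followed by the formula.

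**The concern.** A total depends on how often alarms occur and on how long the patient is observed. Here observation ends at extubation, which happens after randomisation and whose timing is itself compared between the arms. An analyst who follows the analysis paragraph literally would not estimate outcome 11. The result would combine the alarm rate with the time spent ventilated inside the window.

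If one arm has more extubations before three hours, its mean total falls in proportion to its shorter mean observation, even when the hourly rates are identical. A reader of eTable 5 could take that difference for a lower alarm burden. The primary outcome is not affected.

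**Working it through.** The documents give no alarm rate and no share of patients extubated before three hours, so there is no stated figure to reproduce. The check compares the definitions and then shows how the artefact scales under assumed inputs.

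**Definitions side by side**

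| Place | Quantity | Corrected for observed time? |
|---|---|---|
| Outcome 11 | count per hour | yes |
| Analysis paragraph | total count in window | no step stated |
| eTable 5, three-hour rows | n/3 hours | unclear, no scaling rule |
| eTable 5, all recorded time | n/hour | yes, but this serves outcome 12 |

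**Size of the artefact.** Let p be the share of an arm extubated before three hours and h their mean extubation time. Mean observed time is 3 − p × (3 − h) hours. With the same constant hourly rate in both arms, the ratio of mean totals equals the ratio of mean observed times. Both p and h are assumptions.

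| Extubated early | h = 1.5 h | h = 2.0 h | h = 2.5 h |
|---|---|---|---|
| 20% vs 10% | 2.70/2.85: 5.3% lower | 2.80/2.90: 3.4% lower | 2.90/2.95: 1.7% lower |
| 30% vs 10% | 2.55/2.85: 10.5% lower | 2.70/2.90: 6.9% lower | 2.85/2.95: 3.4% lower |
| 50% vs 10% | 2.25/2.85: 21.1% lower | 2.50/2.90: 13.8% lower | 2.75/2.95: 6.8% lower |
| equal shares, same h | 0% | 0% | 0% |

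In counts, at h = 2.0 and 30% versus 10%, the difference is rate × (2.70 − 2.90). That is −1.0 alarm at an assumed 5 per hour and −2.0 at 10 per hour. At 50% versus 10% it is −2.0 and −4.0.

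**Effect on the test.** The simulation used 98 patients per arm (half of the planned 196) and 3,000 runs per scenario. Counts were gamma-Poisson at 5 or 10 alarms per hour, with a between-patient coefficient of variation of 0.5 or 1.0. Early extubation was uniform on 1 to 3 hours. True hourly rates were equal, so a two-sided 5% test should reject in about 5% of runs.

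| Extubated early | t-test on totals rejects |
|---|---|
| 10% vs 10% | about 5% |
| 20% vs 10% | 5-7% |
| 30% vs 10% | 7-15% |
| 50% vs 10% | 15-44% |

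The t-test on count divided by observed hours rejected in 4.3-5.9% of runs across all these scenarios, and its mean difference was close to zero.

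**The case against.** The strongest reply is that the analysis paragraph is shorthand. It repeats outcome 11 almost word for word, and no text gives it precedence over the outcome definition. Similarly, n/3 hours sits beside n/hour in the same notation and could mean a rate scaled to three hours, which is outcome 11 multiplied by three. Both readings are possible. However, the plan states no scaling rule, and its only operational instruction names the total. Two analysts could follow the document and produce different numbers.

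A second reply is that eTable 5 also reports n/hour over all recorded time. That row answers outcome 12, for which no analysis paragraph is written, and it does not repair the three-hour comparison.

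Several objections stand and limit the point:

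- A reader might infer that the alarm comparison will be biased, or biased in favour of INTELLiVENT-ASV. The documents do not support this. Spontaneous breathing trials were not applied in either arm during the first three hours, the physician made the extubation decision, and no early-extubation share is given. Quickwean was active from admission in one arm, so a difference is possible, but no passage predicts one inside the window.
- A reader might fault the t-test for skewed counts. The bootstrap check and the distributional fallback already address shape, although neither adds exposure time.
- A reader might assume that lower workload is part of the trial's case for the mode. The documents only list alarms and interactions among the secondary endpoints.

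**Conclusion.** The mismatch is explicit, and the rule is wrong as written: executing it would not estimate the outcome that the plan defines. Whether this produces a misleading result depends on whether observed time inside the window differs between arms, which cannot be known from the documents. Under the assumed shares and extubation times, the artefact runs from about 2-5% (20% versus 10%) to 7-21% (50% versus 10%). It vanishes with equal exposure and may be small in practice.

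The calculation assumes a constant hourly rate within the window. If alarms cluster around waking or extubation, an hourly rate still depends partly on when observation stops, but it would at least be the quantity named in outcome 11. This is a secondary outcome, and the correction is worth making because it is nearly free and can change the estimate.

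**What to change.** 1. In the analysis paragraph, state that the variable is each patient's number of alarms (and, separately, interventions) divided by that patient's observed ventilated hours in the window. The planned t-test, bootstrap and fallback can stay.
2. Optionally, use a negative binomial or quasi-Poisson model with log observed hours as offset and report a rate ratio with 95% CI. This gives less weight to patients with very short observation, but it is not needed to remove the artefact.
3. Apply the same rule to outcome 12, which has rows in eTable 5 but no analysis text.
4. In eTable 5, change the three-hour rows for alarms and interventions to n/hour.
5. As a separate alignment, report SpO₂ below 85% in eTable 5 as a percentage of recorded breaths. Outcome 20 defines it that way, whereas the table shows numbers of times per three hours and per hour.

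The cost is a few sentences and row labels. The SAP states that it precedes database lock, and the datalogger already records ventilation breath by breath, so observed time per patient should be available without new data collection.
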